3.2.4.3 Additional endpoints from subject eDiary

To assess the effect of tezepelumab on other asthma control metrics, additional questionnaires to the ASD will be administered to collect rescue medication, night-time awakening and total daily asthma symptom score.

The total daily asthma symptom score is derived from the Global Asthma Symptom items assessment each morning and evening, used for the alerts system. This is not the same as the total score derived from the ASD.

The following endpoints will be derived:

- weekly mean rescue medication use
- weekly mean number of night-time awakenings requiring rescue medication
- weekly mean total daily asthma symptom score
- weekly mean daytime asthma symptom score
- weekly mean night-time asthma symptom score

In the endpoints described in this section, where relevant, one day is defined as the evening measurement followed by the measurement the following morning.

Rescue medication use

The number of rescue medication inhalations and nebulizer treatments taken will be recorded by the subject in the eDiary twice daily. Daytime use is recorded in the evening and night-time use is recorded in the morning. Inhaler usage will be reported as the number of puffs in a given period whereas nebulizer use will be reported as the number of times.

The number of inhalations of rescue medication and nebulizer treatments captured in the eDiary each day will be calculated per subject. If a subject is missing a value for either night-time or daytime rescue medication on a given day (evening followed by morning), then the total rescue medication use for that day will be set to missing.

The daily rescue medication use will be calculated as follows:

Number of night inhaler puffs + 2 x [number of night nebulizer times] + number of daytime inhaler puffs + 2 x [number of day nebulizer times].

Change from baseline in the weekly mean of the daily rescue medication use will be calculated at each post-baseline week.

Night-time awakenings that required rescue medication

Change from baseline in the percentage of available nights within the week for which there was an awakening due to asthma that required rescue medication will be calculated at each post-baseline week.

Total daily asthma symptom score

Asthma symptoms during night-time and daytime will be recorded by the subject each morning and evening in the eDiary. Symptoms will be recorded using a scale 0-3, where 0 indicates no asthma symptoms. Asthma symptom daytime score (recorded in the evening), night-time score (recorded in the morning) and total score will be calculated and presented separately.

The total daily asthma symptom score will be calculated by taking the sum of the daytime score recorded in the evening and the night-time score recorded the following morning. If a subject is missing a value for either night-time or daytime asthma symptom score on a given day (evening followed by morning), then the total score for that day will be set to missing.

For weekly mean scores derived from subject eDiary, baseline is defined in [Section 3.1.1](#). The weekly mean calculations and rules for missing days are similar to those for ASD in [Section 3.2.2.4](#).

3.2.4.4 Home-based peak expiratory flow

Change from baseline in weekly mean morning and evening peak expiratory flow (PEF) will be calculated separately.

Home PEF testing will be performed by the subject in the morning upon awakening (and prior to taking their AM asthma controller) and in the evening at bedtime (and prior to taking their PM asthma controller). Subjects should perform 3 successive peak flow manoeuvres while sitting or standing, but in the same position at every testing. The best (highest) morning and evening PEF will be derived from the available individual PEF measurements on each day in the morning and evening respectively.

For weekly means derived from home-based PEF, baseline is defined in [Section 3.1.1](#). The weekly mean calculations and rules for missing days are similar to those for ASD in [Section 3.2.2.4](#).

3.2.4.5 Health resource utilisation

Health care resource utilisation due to asthma will be recorded in the “Asthma-Related Events since Previous Visit” module of the eCRF.

Planned treatment period number of days/times and on-study number of days/times will be calculated for each subject for the following variables:

- Ambulance transport
- Hospitalisation
- Intensive care (days in intensive care)

- General care (days in general care)
- Emergency room visit
- Hospital admission or emergency department > 24 hours
- Visit to specialist
- Visit to primary health care physician
- Other health care visit
- Home visit, physician
- Home visit, other health care
- Telephone call, physician
- Telephone call, nurse
- Telephone call, other physician/health care provider
- Spirometry
- Advanced pulmonary function test
- Plain chest X-ray
- Computer tomography
- Oxygen initiated

The planned treatment period number per subject will be determined as:

Planned treatment period number = Sum of 'number of times/days' as entered on the eCRF page up to Week 52.

The on-study number per subject will be determined as:

On-study number = Sum of 'number of times/days' as entered on the eCRF page up to Week 64.

3.2.4.6 Work productivity and activity impairment

The WPAI+CIQ questionnaire is a 10-item questionnaire that assesses productivity and activity impairment over the previous week.

There are a maximum of 10 questions and a minimum of 3 questions that will be completed by subjects as follows:

1. Currently employed (yes/no)
2. Hours missed work due to health problems
3. Hours missed work due to other reasons
4. Hours actually worked
5. Degree health affected productivity while working (0-10 scale, with 0 meaning no effect)
6. Attends class in an academic setting (yes/no)
7. Hours missed class due to health problems
8. Hours actually attended class
9. Degree health affected productivity while attending class (0-10 scale, with 0 meaning no effect)
10. Degree health affected regular activities (other than work or class) (0-10 scale, with 0 meaning no effect)

If the answer to question 1 is 'No, not currently employed', then the subject should skip to question 6. If the answer to question 6 is 'No, not currently attending class', then the subject should skip to question 10.

The WPAI+CIQ provide 4 scores:

- Absenteeism (work or class time missed)
- Presenteeism (impairment at work or class/reduced on-the-job effectiveness)
- Work productivity loss (overall work or class impairment/absenteeism plus presenteeism)
- Activity impairment

WPAI+CIQ outcomes are expressed as impairment percentages, with higher numbers indicating greater impairment and less productivity.

For each time point at which the WPAI-CIQ is administered, the following descriptive

statistics (if applicable) (n, total number of hours, mean per subject, standard deviation (SD), median, minimum and maximum) will be reported for those who are employed:

- # employed
- % of all subjects employed
- # of work hours missed due to asthma
- Absenteeism due to asthma
- Presenteeism due to asthma
- Work Productivity Loss
- Activity impairment

The following formulae will be used to calculate each of the outcome measures listed above:

- # currently employed – Yes in response to Question 1
- # of hours missed due to asthma – as responded in Question 2
- Absenteeism = $Q2/(Q2+Q4)$
- Presenteeism = $Q5/10$
- Work Productivity Loss = $Q2/(Q2+Q4)+[(1-Q2/(Q2+Q4))x(Q5/10)]$
- Activity Impairment = $Q10/10$

Similarly, the following will be reported for those subjects who are in school:

- # in school
- % of all subjects in school
- # of class hours missed
- Absenteeism due to asthma
- Presenteeism due to asthma
- Class Productivity Loss
- Activity impairment

The following formulae will be used to calculate each of the outcomes measures listed above:

- # in school - Yes to Question 6
- # of class hours missed due to asthma – as responded on Question 7
- Absenteeism due to asthma - $Q7/(Q7+Q8)$
- Presenteeism due to asthma – $Q9/10$
- Class Productivity Loss – $Q7/(Q7+Q8) + [(1-Q7/(Q7+Q8))x(Q9/10)]$
- Activity Impairment = $Q10/10$

In addition, activity impairment will be presented for those who are not employed, not in school, and all subjects.

3.2.4.7 EQ-5D-5L score

The EQ-5D-5L questionnaire assesses 5 dimensions: mobility, self-care, usual activities, pain/discomfort and anxiety/depression. Each dimension has 5 response options (1 = no problems, 2 = slight problems, 3 = moderate problems, 4 = severe problems, and 5 = extreme problems) that reflect increasing levels of difficulty.

The subject will be asked to indicate his/her current health state by selecting the most appropriate level in each of the 5 dimensions. The questionnaire also includes a visual analogue scale (VAS), where the subject will be asked to rate current health status on a scale of 0 - 100, with 0 being the worst imaginable health state.

The health state valuation (an index-based value) for the EQ-5D-5L will be derived from the 5 dimensions using the UK population-based preference weights. Further details are given in [van Hout et al., 2012](#) and [Devlin et al., 2017](#).

The change from baseline in VAS, health state valuation index and the 5 dimensions above will be calculated for each post-baseline time point.

3.2.4.8 Patient and clinician global impression scores

The Clinical Global Impression of Change (CGI-C) and Patient Global Impression of Change (PGI-C) instruments are used to evaluate the overall response to treatment. For the CGI-C the investigator (clinician) will be asked to rate the degree to which the overall asthma status may have changed when compared to baseline. The assessment uses a 7-point rating scale: 1 = Very Much Improved; 2 = Much Improved; 3 = Minimally Improved; 4 = No Change; 5 = Minimally Worse; 6 = Much Worse; 7 = Very Much Worse. The PGI-C asks subjects to report change from baseline using the same scale as the CGI-C.

The Patient Global Impression of Severity (PGI-S) is a single item designed to capture the subject's perception of overall symptom severity at the time of completion using a 6-point categorical response scale (0 = No Symptoms; 1 = Very Mild Symptoms; 2 = Mild Symptoms; 3 = Moderate Symptoms; 4 = Severe Symptoms; 5 = Very Severe Symptoms).

For CGI-C and PGI-C subjects will also be categorized as Improved, Much Improved and Very Much Improved according to the following responses post-baseline:

- Improved: subjects in this category will include those with responses of 'very much improved', 'much improved' and 'minimally improved'.
- Much Improved: subjects in this category will include those with responses of 'very much improved' and 'much improved'.
- Very Much Improved: subjects in this category will include those with responses of 'very much improved'.

Subjects can be counted in more than one category at a given time point.

Calculation of percentages will be based on the number of subjects in the FAS with a completed assessment. There will be no imputation for missing values.

3.2.5 Exploratory endpoints

CCI [REDACTED]

[REDACTED]

[REDACTED]

[REDACTED]

[REDACTED]

[REDACTED]

[REDACTED]

[REDACTED]

[REDACTED]

[REDACTED]

[REDACTED]

CCI

[Redacted text block containing multiple paragraphs of information, including a list of items and a table structure. The text is obscured by black bars.]

CCI

[Redacted]

[Redacted]

[Redacted]

[Redacted]

[Redacted]

[Redacted]

[Redacted]

[Redacted]

[Redacted]

[Redacted]

[Redacted]

[Redacted]

[Redacted]

[Redacted]

[Redacted]

CCI [Redacted]

[Redacted]

[Redacted]

[Redacted]

[Redacted]

[Redacted]

[Redacted]

[Redacted]

[Redacted]

[Redacted]

[Redacted]

[figure not shown]
[Redacted]

[Redacted]

[Redacted]

[Redacted]

CCI

[Redacted text block]

[Redacted text block]

[Redacted text block]

[Redacted text block]

[Redacted text block]

3.3 Derivation of safety variables

3.3.1 Exposure to IP and treatment compliance

Extent of exposure to IP is defined as the number of days between the date of first dose of IP and the date of last dose of IP inclusive plus the number of days allowance for the dosing interval specified in [Section 2.1.5](#), that is:

$$\text{Extent of exposure (days)} = \text{minimum (date of last dose of IP + 33 days; date of death; date of study withdrawal)} - \text{date of first dose of IP} + 1$$

This calculation does not consider any gaps in exposure caused by the subject missing one or more intermediate scheduled 4-weekly doses. Such cases will be identified in the CSR if they occur, but will not explicitly be accounted for in any analysis.

The total subject-years exposure for a treatment group will be derived as the sum of the individual subject extents of exposure (days) for that treatment group and divided by 365.25.

Treatment compliance will be calculated as follows:

$$\text{Treatment compliance (\%)} = \left[\frac{\text{Total number of actual dosing occasions}}{\text{total number of expected dosing occasions}} \right] \times 100\%$$

In order to allow for subjects who discontinue IP early in the compliance calculation, the number of expected dosing occasions will be calculated as the number of scheduled dosing visits up to and including the last available dosing visit for that subject.

3.3.2 Adverse events – general

Adverse events (AEs) experienced by any subject at any time during the entire study will be coded using the latest version of the Medical Dictionary for Regulatory Activities (MedDRA).

AEs will be categorised for analysis according to their onset date into the following study periods:

- AEs occurring during screening/run-in period: date of Visit 1 \leq AE onset date < date of first dose of IP
- AEs occurring during on-treatment period: date of first dose of IP \leq AE onset date \leq minimum (date of last dose of IP + 33 days, date of death, date of study withdrawal)
- AEs occurring during post-treatment period (for subjects still being followed up then): date of last dose of IP + 33 days < AE onset date \leq study completion or withdrawal date
- AEs occurring during on-study period: date of first dose of IP \leq AE onset date \leq study completion or withdrawal date.

In the above, note that for subjects entering the extension study, the study completion date will be the day of enrolment in the extension study.

If the AE has a completely missing (and unresolvable) onset date, then the AE will be assumed to have occurred during the on-treatment period, unless the end date indicates unambiguously that the AE resolved before treatment started.

If the AE has a partially missing (and unresolvable) onset date, then the AE will also be assumed to have occurred during the on-treatment period, unless either the end date indicates

unambiguously that the AE resolved before treatment started, or the partial onset date is in the month/year prior to start of treatment.

Exposure adjusted incidence rates will be defined as the number of subjects reporting adverse events divided by extent of exposure for each subject, where exposure will be defined (irrespective of whether they have had the AE) as in 3.3.1 for extent of exposure for the on-treatment summaries.

Study adjusted incidence rates will be defined as the number of subjects reporting adverse events divided by duration of the on-study period for each subject as defined in [Section 3.1.2](#).

The total time at risk (years) for a treatment group will be derived as the sum of the individual subject times at risk (days) for that treatment group and divided by 365.25.

For exposure-adjusted summaries of all AEs, the time at risk for each subject will be calculated using the first formula based on date of last dose of IP for all subjects, irrespective of whether they have had the AE.

In all exposure-adjusted summaries of AEs, multiple occurrences of the same event for a particular subject will not be counted as separate events. A subject will either be considered to have no events of the type being summarised, or one or more occurrences of that event.

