3. If the subject cannot or does not wish to comply with any of the options above, (or any component of them such as only telephone based visits without completion of the diary and ePEF), they will complete a follow-up visit at 16 weeks (+/-5 days) (refer to SoA, Visit 19 – week 64) post last IP administration. After this visit the Investigator

will only contact the subject at 52 weeks post-randomization. No other study assessments will be performed prior to this contact.

If the last IP administration was after week 36 for options 1 or 2, the subject will return to the clinic for an EOT visit at Week 52 (+/- 5 days), and for option 3, the investigator will contact the subject at 52 weeks post randomization. The subject for options 1, 2 and 3 will then return for a follow-up visit 16 weeks (+/- 5 days) post last IP administration (refer to SoA, V19 – Week 64).

The EOT visit will be completed immediately in the case of subsequent early withdrawal from option 1 or 2. Subjects who do not wish to have any follow-up contacts will be discontinued from the study. All discontinued subjects must return the diary and ePEF devices at the EOT visit.

If the subject chooses option 1, all assessments will be completed as per the SoA as indicated in Section 1.1. If the subject chooses 2 or 3, the key information to be collected during the telephone calls are AEs/SAEs, changes in concomitant medication, health care utilization, and asthma exacerbation information.

Subjects who initially choose options 1 or 2 and subsequently cannot or do not wish to comply with the requirements of their option can continue with a less intensive option (i.e. subject initially choosing option 1 can continue with options 2 or 3, subjects initially choosing option 2 can continue with option 3).

If a subject discontinues IP due to a study specific discontinuation criterion, this should always be recorded as 'Development of study specific discontinuation criteria' on the Discontinuation of Investigational Product form in the eCRF.

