3.1.6 Prior and concomitant medication

Medications taken by any subject at any time during the study will be coded using the ATC classification system within the WHO Drug Dictionary.

Medications will be categorised for analysis according to their onset and end dates as follows:

- Prior medications:
 - end date \leq date of first dose of IP
- Concomitant medications during on-treatment period:
 - end date $>$ date of first dose of IP and start date \leq minimum (date of last dose of IP + 33 days, date of death, date of study withdrawal), or
 - end date ongoing and start date \leq minimum (date of last dose of IP + 33 days, date of death, date of study withdrawal)
- Concomitant medications during post-treatment period (for subjects still being followed up then):
 - start date $>$ date of last dose of IP + 33 days.

Essentially the above says that:

- Prior and concomitant medications are mutually exclusive.
- Concomitant medications on-treatment and post-treatment are also mutually exclusive (here, the word “concomitant” means concomitant with study procedures, irrespective of whether IP was still being taken). Specifically, a concomitant

medication which started on-treatment and ended post-treatment will only be considered on-treatment.

If the medication record has a completely missing onset date, the subject will be assumed to have been on the medication on the date of the first study procedure. If the medication record has a partially missing onset date (month/year or year only) which is the same as that for the end of IP treatment, it will be assumed to have started on-treatment. If the medication record has a partially missing onset date (month/year or year only) which is the same as that for the start of IP treatment, it will be assumed to have started before treatment.

If the medication record has a completely missing end date, the subject will be assumed to have been on the medication on the date of study completion or withdrawal. If the medication record has a partially missing end date (month/year or year only) which is the same as that for start of IP treatment, it will be assumed to have ended on-treatment. If the medication record has a partially missing end date (month/year or year only) which is the same as that for end of IP treatment, it will be assumed to have ended post-treatment.

In the above, note that for subjects entering the extension study, the study completion date will be the day of enrolment in the extension study.

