4.2.8.1 Adverse events

AEs will be summarised separately for the on-treatment and on-study periods as defined in [Section 3.1.4](#) unless stated otherwise. All AE summaries will be presented by treatment group. AEs occurring during the screening/run-in period, or occurring post-treatment will be listed, but not summarised separately.

An overall summary table will be produced showing the number and percentage of subjects with at least one AE in each of the following categories: any AEs, serious adverse events (SAEs), AEs with a fatal outcome, AEs leading to discontinuation of IP (DAEs), and adverse events of special interest (AESIs). The total number of AEs in the different AE categories will also be presented as well as the number of subjects (i.e. accounting for multiple occurrences of the same event in a subject).

All AEs will be summarised by system organ class (SOC) and preferred term (PT) assigned to the event using the MedDRA dictionary. For each PT, the number and percentage of subjects reporting at least one occurrence of the event will be presented (i.e. subjects with multiple occurrences of the same PT will only be counted once).

Similar summaries by SOC and PT will also be presented for:

- SAEs
- Fatal AEs
- DAEs
- DAEs causally related to IP
- SAEs leading to discontinuation of IP

- Each AESI category separately
- The most common AEs (defined as those occurring in >3% of subjects in either treatment group) – by PT only

All AEs (by PT) will be summarised additionally by causality and maximum intensity. If a subject reports multiple occurrences within each SOC and PT, the maximum intensity will be taken as the highest recorded (the order being mild, moderate and severe) respectively.

In addition, each AESI category will be summarised by causality.

The AESI of injection site reactions will be further summarised by:

- Site of injection (arm, thigh, abdominal wall)
- Total number of doses administered (1, 2, ..., 13), irrespective of timing of the injection site reaction event.

Exposure-adjusted AE summaries will be presented by SOC and PT for each of the following (on-treatment summaries only):

- All AEs
- Each AESI separately

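### The SAP's rule for partial adverse event onset dates counts an event as on-treatment even when its recorded month or year lies wholly after the on-treatment period

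*SAP*

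**What the plan says.** SAP 3.3.2 sorts AEs into periods by onset date. The on-treatment period ends at the earliest of last dose + 33 days, death and study withdrawal. The post-treatment period follows it, with the lower bound "date of last dose of IP + 33 days < AE onset date".

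For incomplete onset dates that cannot be resolved, the section gives a default: "If the AE has a partially missing (and unresolvable) onset date, then the AE will also be assumed to have occurred during the on-treatment period". It then lists two exceptions. The default does not apply when the end date shows "unambiguously that the AE resolved before treatment started, or the partial onset date is in the month/year prior to start of treatment". Both exceptions concern the start of treatment, and nothing is said about its end.

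SAP 3.3.1 stops exposure at the same end date as the on-treatment period. For the exposure-adjusted summaries, SAP 3.3.2 adds that "the time at risk for each subject will be calculated using the first formula based on date of last dose of IP", whether or not the subject had the event. SAP 4.2.8.1 restricts those summaries to on-treatment AEs, for all AEs and for each AE of special interest (AESI). Post-treatment AEs appear only in listings, although they do count in the on-study tables. Protocol 8.3.2 has AEs collected through follow-up, so such events can arise.

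**The concern.** A default to on-treatment is sensible when a partial date could fall in either period. Here the recorded month or year excludes the on-treatment period, and the same section gives the event two classifications: post-treatment by definition and on-treatment by the partial-date rule.

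The event then enters a numerator whose denominator contains none of the time in which it occurred. The rule is not reliably conservative for a comparison either. A misplaced event on tezepelumab raises that arm's rate, while one on placebo raises the placebo rate and can hide a difference. What is at stake is the accuracy of on-treatment safety tables, chiefly for rare AESIs. No efficacy analysis or confirmatory test is involved.

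**Working it through.** The plan gives no figure to reproduce, so the check applies the rule as written and then the same rule with one added exception.

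**Inputs.** Target days are from SAP 3.1.5: Week 24 = Day 169, Week 52 = Day 365, Week 48 = Day 337, Week 64 = Day 449. The 33-day allowance is from SAP 2.1.5 and 3.3.1. Follow-up after early discontinuation is from Protocol 7.1.1. A first-dose date of 10 January 2019 is assumed, to turn days into calendar months.

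**Formulas.** On-treatment end = last dose day + 33. Post-treatment days = last follow-up day − on-treatment end. Exposure = on-treatment end − first dose day + 1, with first dose on Day 1.

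| Subject | On-treatment end | Last follow-up | Post-treatment days | Exposure (days) | Months wholly after on-treatment end |
|---|---|---|---|---|---|
| Completer, not entering the extension | 337 + 33 = 370 | 449 | 79 | 370 | 3 (Feb–Apr 2020) |
| Last dose at Week 24 | 169 + 33 = 202 | 365 | 163 | 202 | 6 (Aug 2019–Jan 2020) |
| First dose only | 1 + 33 = 34 | 365 | 331 | 34 | 11 (Mar 2019–Jan 2020) |

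Under the rule as written, a month-only onset in any month of the last column is on-treatment. With the added exception it is post-treatment. Nothing else moves. For example, the completer's on-treatment period ends on 14 January 2020, so an onset recorded as January 2020 overlaps it and stays on-treatment under both versions.

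**Effect on an exposure-adjusted rate.** Assume 530 subjects per arm with 370 days each: 530 × 370 / 365.25 = 536.9 subject-years. The number of misplaced subjects is also assumed, at 1 or 2. Rate per 100 subject-years = 100 × subjects / 536.9.

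| Subjects truly on-treatment | None misplaced | 1 misplaced | 2 misplaced |
|---|---|---|---|
| 5 | 0.93 | 1.12 | 1.30 |
| 50 | 9.31 | 9.50 | 9.69 |

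**Comparison within the SAP.** For medications, SAP 3.1.6 takes a partial onset as on-treatment when its month/year, or year, matches that of the end of IP treatment. That rule refers to the end of treatment; the AE rule does not. The medication text does not say what happens to later partial onsets, so it shows that the end date was considered there but does not supply the missing AE rule.

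**The case against.** The strongest reply is that little turns on this. The rule reaches only dates that remain unresolvable, and Protocol 8.3.4 lists the AE start date among the variables to collect. Preferred-term tables and exposure-adjusted rates count a subject once per event type, so a misplaced AE changes them only if the subject had no on-treatment occurrence of that type. On-study tables are produced alongside, and the event belongs in them either way. Malignancies, one of the rare categories, are also adjudicated. All of this stands and limits the impact. None of it removes the misclassification.

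A reader might infer more than the documents support:

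- **That the events occur off drug.** Protocol 8.4.2.2 equates 16 weeks with five half-lives. A completer's follow-up from Week 48 to Week 64 is exactly 16 weeks, so drug may still be present. The accurate description is after the SAP on-treatment period.
- **That subjects choosing the least intensive follow-up are seen only at Week 52.** The investigator "will only contact the subject at 52 weeks post-randomization", but only after a visit 16 weeks post last dose, and there is also a discontinuation visit at 4 weeks. With last dose on Day 85, these fall near Day 85 + 28 = 113 and Day 85 + 112 = 197. An AE near Day 300 would be asked about some 65 days later. The documents do not say that partial dates are commoner in these subjects.
- **That the error differs between arms.** Nothing in the documents indicates differential discontinuation.
- **That a count of misplaced AEs can be projected.** It would need an AE rate, a partial-date share and an IP discontinuation rate, none of which is given. The 10% in Protocol 9.2 is a dropout rate for the sample size.
- **That the phrase "it will be assumed to have ended post-treatment" in SAP 3.1.6 is the parallel rule.** It governs medication end dates. The relevant comparison is the onset sentence described above.

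**Conclusion.** Wrong as written, with minor impact. The textual gap is certain: the rule has no exception at the end of treatment, it contradicts the post-treatment definition in its own section, and no other section corrects it. The practical effect depends on the number of unresolvable onset dates that fall wholly after the on-treatment period. The documents do not give that number, and it is probably small. Common events barely move. A rare AESI is where one misplaced subject would be visible, and the illustrative rates for this rest on assumed full exposure and assumed misplacement. The on-treatment default itself is reasonable for a partial date that overlaps the on-treatment period.

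**What to change.** Add a third exception to the partial-date rule in SAP 3.3.2: *or the partial onset date (month/year, or year) is wholly after the end of the on-treatment period, in which case the AE is assigned to the post-treatment period*. State that the on-treatment default applies only when the partial date overlaps the on-treatment period. In practice the exception matters where last dose + 33 days sets the end date, since death or withdrawal also ends follow-up.

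The cost is one clause in the SAP and one line of derivation code. No data collection, analysis set or efficacy analysis changes. A blinded count of AEs with unresolvable partial onset dates before the primary database lock would show whether any table is affected.
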